4.3 Recruitment of Participants

We will recruit healthy adult normal volunteers for the Dosimetry group and Rest/Stress group from the community through the Research Participant Registry/Volunteer for Health (VFH) Program at Washington University in St. Louis (<https://vfh.wustl.edu>).

Study patients enrolled in the rest/stress group will be for the assessment of the efficacy of ⁶⁸Ga-Galmydar. Patients referred for routine SPECT MPI in the Division of Nuclear Medicine or from the cardiology inpatient/outpatient clinics at Barnes-Jewish Hospital/Washington University in St. Louis will be recruited.

Participants' electronic health records (EHR) will be accessed to review general health information for contraindications to planned study procedures and confirm pre-eligibility. A study team member will call potential subjects to discuss the study and answer any questions. Participants who verbally agree to participate will be scheduled for study visits.

4.4 Study Enrollment

Upon arrival to the imaging facility, participants will be provided the informed consent for review. The study coordinator will review the informed consent form with the participant and address any questions or concerns prior to obtaining written consent or performing any research procedures. Participants must be willing and able to undergo all procedures.

Imaging will begin with the healthy adult normal volunteers enrolled in the dosimetry group. The first two, (2) normal volunteers will be separated by 2-3 days to ensure participant safety data is ascertained during the post-injection phone follow-up. Upon completion of the review, the study will continue with imaging of the remaining dosimetry subjects with simultaneous entry of the rest/stress group.

4.4.1 Dosimetry Group

Eight healthy adult normal volunteers (4 males and 4 females) will be enrolled in the dosimetry group and undergo whole-body PET/CT imaging with ⁶⁸Ga-Galmydar.

4.4.2 Rest/Stress Group

For the rest/stress group, we will recruit 30 subjects. The first set will be symptomatic patients (n=20) who have undergone a SPECT MPI examination. Half of these patients will have had a study positive for ischemia in two myocardial segments and referred for invasive coronary angiography (ICA) as part of their routine standard-of-care (n=10). Subjects will undergo [⁶⁸Ga]Galmydar PET/CT prior to any intervention. The second half of these patients will have had a normal SPECT MPI and no ICA referral (n=10). A second set of subjects who are normal, asymptomatic, and without a history of cardiovascular disease will serve as controls (n=10).

4.5 Early Discontinuation of Participants

The Principal Investigator or designee may prematurely discontinue a participant at any time if the constraints of the protocol are considered to be not in the best interest of the participant, i.e., increased risks jeopardizes the safety of the participant. Reasons maybe related to an adverse event that in the opinion of the Principal Investigator or designee requires the participant should be withdrawn. Other reasons may include non-compliance with study procedures, lost to follow-up, or a positive pregnancy test.

Participants who develop hypertension, hypotension, or other adverse event secondary to the regadenoson administration during the PET/CT MPI stress component and if in the Principal Investigator or designee's opinion the enrolled participant is deemed ineligible to safely undergo the stress ¹³N-ammonia PET study, the participant may be allowed to continue participation. The stress portion of the ¹³N-ammonia PET study will be removed. The participant will only undergo the rest portion of the ¹³N-ammonia PET study.

4.6 Premature Withdrawal and Replacement of Participants

Any participant who no longer wishes to continue participation may withdraw consent at any time and for any reason without prejudice. Withdrawal will not interfere with routine clinical care. Participants are informed to contact a study team member, e.g., study coordinator or by sending a withdrawal letter to the Principal Investigator or designee as listed in the Informed Consent Form. Attempts will be made to discuss with the participant the reasons for withdrawal and the importance of the study evaluations.

Include documentation of reason(s) for discontinuation or withdrawal in the enrollment log. Withdrawn participants are not allowed to re-enroll into the study. Participants who do not complete all protocol-required procedures are replaced to ensure adequate evaluable data.

5 INVESTIGATIONAL STUDY DRUG

5.1 Drug Description

The investigational study drug is ⁶⁸Ga-Galmydar. Gallium-68 is a positron-emitting radioisotope that is produced from a ⁶⁸Ge/⁶⁸Ga generator with a physical half-life of 67.7 minutes. An Investigator's Brochure does not exist for this radioactive drug. The pharmacological properties and formulation are described in detail in the Chemistry, Manufacturing, and Control Data section of the IND application.

5.2 Drug Handling, Preparation, and Release

Handling of all radioisotopes will be conducted under the auspices of the Radiation Safety Office at Washington University School of Medicine (WUSM). [⁶⁸Ga]Galmydar will be produced under the leadership of the Director of the WUSM Cyclotron Facility, and under the supervision of the Associate Director of the Cyclotron Production and the Director of the Radiopharmacy. Trained personnel perform the preparation and quality control tests for the release of [⁶⁸Ga]Galmydar under the supervision of the radiopharmacist in charge.

5.3 Drug Administration

The Sponsor-Investigator will adhere to the procedures and requirements in accordance with applicable policies of the Radiation Safety Committee (RSC) at Washington University and the U.S. Nuclear Regulatory Commission (NRC).

A PET-certified medical professional will draw, administer, and assay the dosage in a dose calibrator before and after the administration of all radiotracers.

The Dosimetry group will receive one single intravenous administration of $8 \text{ mCi} \pm 20\%$ (6.4–9.6 mCi) of ⁶⁸Ga-Galmydar. The Rest/Stress Group will receive two intravenous administrations of ⁶⁸Ga-Galmydar, $4 \text{ mCi} \pm 20\%$ (3.2–4.8 mCi) during rest and $6 \text{ mCi} \pm 20\%$ (4.8–7.2 mCi) during the stress of [⁶⁸Ga]Galmydar on the PET MPI Imaging Day-1. The acceptable mass for each [⁶⁸Ga]Galmydar administration is $\leq 10 \text{ } \mu\text{g}$. On Imaging Day-2, subjects will receive two single intravenous administrations each of $10 \text{ mCi} \pm 20\%$ (8–12 mCi) of N-13 Ammonia.

5.3.1 Dosage Variance

If a required administered dosage is outside the allowable range because of unforeseen circumstances, i.e., lack of radiopharmaceutical activity, an authorized user physician before administration of the tracer must approve a dosage in writing or verbally as a variance. The authorized user must provide written approval to the imaging facility within 48-hours after a verbal approval. All members of the research team will comply with the Washington University Radiation Safety Committee Policy on Dispensing of Radiopharmaceutical Dosages for Human Research Subjects.

6 STUDY PROCEDURES

The Schedule of Activities (SoA) tables for the Dosimetry group and Rest/Stress group summarizes the study assessments and procedures, see [Attachments](#). The results of all assessments and evaluations will be recorded on the case report forms. The PI or sub-investigator delegated by the PI will review screening and evaluations to confirm eligibility criteria of all enrolled subjects. The research study team will maintain study logs, e.g., screening and enrollment logs of participants with details of screen failures, dropouts and adverse event log.

6.1 Screening Assessments

The coordinator will review the informed consent form and address questions or concerns with the participant and family/friends. Relevant medical history includes current and past diseases/illnesses and concurrent medications, as well as surgical and family medical history. A brief physical exam will be conducted by the Principal Investigator or designee. A designee is one who is a qualified, engaged member and protocol trained to assess participants. Exams are performed at baseline prior to the [⁶⁸Ga]Galmydar injection to determine if the participant is suitable to undergo study procedures and for subject readiness prior to discharge from the imaging center.

Screening will include the following procedures and evaluations to ensure participants meet inclusion and exclusion criteria.

- Written informed consent will be obtained prior to performing any research procedures;
- Demographics, including gender, date of birth, race, and ethnicity;
- Medical history, including family history and surgical history (e.g., pre-existing conditions and shoulder or chest trauma) as obtained from participants and available medical records, as described below;
- PET/CT contraindications;
- Concomitant medications review, including non-prescription medicines, vitamins, herbs, and supplements;
- Body weight and height measurements;
- A brief physical exam;
- Vital sign measurements, including systolic and diastolic blood pressure, heart rate, and respiratory rate, body temperature;
- 12-lead ECG;
- For women of childbearing potential, a urine pregnancy test must be completed, documented, and confirmed as negative within 24-hrs or on the day of the PET scan. Confirm participant is not breastfeeding and agrees not to become pregnant (refrain from sexual activity or is currently using a medically approved method of contraception) to continue for at least 24-hours post-injection of ⁶⁸Ga-Galmydar;

- Clinical Laboratory Testing: clinical safety labs includes a complete blood count, comprehensive metabolic panel, and urinalysis. All participants will have up to two IV catheters inserted one in each arm. In dosimetry patients, one IV will be used for the collection of blood samples for the lab tests to include serum metabolites, and the second will be used for the administration of ⁶⁸Ga-Galmydar. For patients enrolled in the rest/stress group, one IV catheter will be used for the [⁶⁸Ga]Galmydar administration and the second IV will be used for the administration of the pharmacological stress agent, regadenoson.

6.2 PET/CT Imaging

Imaging will be conducted on the preferred scanner, the Siemens Biograph Vision PET/CT. The Biograph TruePoint/TrueView may be used alternatively in the event of a schedule conflict or scanner problem. The scanners are located adjacent to each other in the Center for Clinical Imaging Research (CCIR) at the Washington University School of Medicine (WUSM) and Barnes-Jewish Hospital (BJH) in St. Louis.

The CCIR allows participants to undergo research-related imaging protocols in a safe environment. The CCIR is fully equipped for the treatment of medical emergencies, including cardiac arrest (crash-cart, intubation equipment, and defibrillator), and is served by BJH emergency code team. The CCIR Facility operates in compliance with the Joint Commission on Accreditation of Healthcare Organization (JCAHO), and the American College of Radiology (ACR). All facilities operate in compliance with the safety guidelines for imaging and for privacy as directed by the Health Insurance Portability and Accountability Act of 1996 (HIPAA) and the Nuclear Regulatory Commission (NRC).

PET radiopharmaceuticals will be produced at Washington University School of Medicine (WUMS)-Mallinckrodt Institute of Radiology (MIR) Cyclotron Facility. For investigational PET drugs for human use produced under an Investigational New Drug (IND) application in accordance with 21 CFR Part 312. WUMS MIR Cyclotron Facility follows the requirement for production of research radiopharmaceuticals in 21 CFR Part 212, Current Good Manufacturing Practice (CGMP) For Positron Emission Tomography Drugs, by complying with the regulations in Chapter <823>, *Radiopharmaceuticals for Positron Emission Tomography (PET)—Compounding, Investigational, and Research Uses*.

6.2.1 PET Imaging Assessments and Preparation

Subjects will be instructed to fast overnight for a minimum of 6-hours prior to the scheduled appointment time. The Rest/Stress group subjects who undergo the stress PET MPI will be instructed to avoid theophylline-containing medication or dipyridamole for at least 48 hours prior to the stress imaging scan. Vasoactive medications such as calcium-channel blockers, angiotensin-converting enzyme inhibitors, β -blockers, and nitrates should be discontinued at least 24 hours before the PET perfusion examination.

The following assessments and procedures will be performed for PET imaging visits:

- Confirm eligibility. Review concomitant medications and any changes in health since the screening if assessments were performed on a separate day. Repeat between imaging days;
- Confirm or perform and document a negative urine pregnancy test for women of childbearing potential for each imaging day;
- Subjects will be requested to use the restroom to empty their bladder prior to radiotracer injection and discharge from the imaging facility;
- Place one peripheral intravenous (IV) catheter for the administration of radiotracer injection and draw blood samples for safety labs. Both the dosimetry group and the rest/stress group will have a second contralateral IV catheter placed. In the dosimetry group, one IV will be used for collection of safety labs and radiotracer metabolites and one IV will be used for the administration of [⁶⁸Ga]Galmydar. In the rest/stress patients, one IV will be used for the administration of [⁶⁸Ga]Galmydar and one for the administration of the pharmacological stress agent, regadenoson;
- Collect blood and urine samples for clinical safety lab tests for [⁶⁸Ga]Galmydar participants at screening to be used for a baseline pre-injection measurement and repeated after the imaging prior to discharge post [⁶⁸Ga]Galmydar injection and;
- Perform a brief physical exam for [⁶⁸Ga]Galmydar participants. The screening exam may be used for baseline pre-injection measurement and repeated post [⁶⁸Ga]Galmydar administration;
- Place the participant on the imaging table in supine position with both arms positioned above the head. To ensure participant comfort, place a pillow or folded towels under elbows and pillows or foam wedge under legs of the participant to maintain their position for the duration of the scan;
- Place electrodes on the participant's chest for continuous ECG monitoring and capturing of 12-lead ECG. Place a blood pressure cuff on the opposite arm used for the administration of the radiotracer. Continue to monitor ECG-rhythm and HR until imaging is completed;
- Obtain vital sign (VS) measurements and 12-lead ECG at the time points listed below and repeat as needed for [⁶⁸Ga]Galmydar participants. VS include heart rate, respiratory rate, and diastolic and systolic blood pressure, body temperature. Obtain vital signs (BP and HR) and 12-lead ECG as required per clinical protocol for the rest/stress Ammonia PET MPI study.
 - Baseline: VS (BP, HR, RR, and body temperature) and a 12-lead ECG within 60-min prior to injection, repeat if >60-min;
 - Pre-injection: BP, HR, and RR within 15-min;
 - Post-injection: BP, HR, and RR within 5-min and 15-min, and hourly during imaging visit;
 - End of imaging scan: BP, HR, and RR;
 - Prior to Discharge: VS (BP, HR, RR, and body temperature) and a 12-lead ECG.

- Instruct participants to not move arms, head, or bend knees throughout the study to reduce motion artifacts;
- To reduce respiratory motion on the CTAC and stabilize heart rate, have participant lie quietly for 2-3 minutes before acquiring scout image;
- Participants will undergo a CT scan for attenuation correction (CT-AC) (50 mAs). Prior to acquiring each CT-AC, provide participant specific instructions to *not* take deep breaths during the CT-AC acquisition. This is to reduce respiratory motion on each CTAC. During the CT-AC scan, the participants will be instructed to perform normal end-expiration breath-holds;
- After completion of the PET/CT study, alignment of the heart as seen on the PET and the CT images should be inspected. In the case of a misalignment, the heart should be re-aligned manually and image reconstruction repeated to ensure there are no artifacts of attenuation correction created by mis-registration of the CT and PET data. Images will be inspected by the technologists;
- Prior to discharge from the CCIR to home or transfer to the CTRU, confirm participants' contact information for the phone follow-up. Provide the participant study team contact information, (i.e., phone number) should an untoward reaction occur;
- For all regadenoson stress PET MPI studies:
 - A physician (cardiologist) will be present;
 - Obtain 12-lead ECG, BP and HR pre and post regadenoson injection.
 - Obtain BP and HR every minute for at least 10-min post regadenoson injection and monitor ECG rhythm strip.
 - Aminophylline will be readily available to attenuate severe or persistent adverse reactions. Administer slow intravenous injection (50 mg to 100 mg over 30 to 60 seconds) at least 1-minute after radiotracer injection.

6.3 Dosimetry Group - PET/CT Imaging

Healthy adult normal volunteers enrolled in the dosimetry group will come to the Center for Clinical Imaging Research (CCIR) facility, a Washington University facility, located on the 10th floor of Barnes-Jewish Hospital for screening and PET imaging.

The following assessments and procedures will be performed:

- VS, 12-lead ECG, safety labs, and a brief physical exam pre and post injection and prior to discharge from the CCIR to home or transfer to the CTRU as described above;
- All required safety assessments prior to the administration of [⁶⁸Ga]Galmydar and monitor ECG rhythm and HR as described above. Monitor ECG-rhythm and HR during imaging;
- Administer an intravenous bolus injection of 8 mCi ± 20% (6.4–9.6 mCi) with a mass of ≤ 10 µg of [⁶⁸Ga]Galmydar followed by a 10 mL normal saline flush;
- Whole-body PET image acquisition from head to mid-thigh. Imaging of subjects will be at three time points spanning from immediately after injection up to 4-hours after

[⁶⁸Ga]Galmydar injection. A low-dose spiral CT scan (120 kVp, 50 mAs) will be obtained for attenuation correction. Begin whole-body PET image acquisition from the head to mid-thigh immediately post [⁶⁸Ga]Galmydar injection for 60-min and repeat at 2 hours and 4 hours.

6.4 Rest/Stress Group - PET/CT Imaging

On Imaging Day-1, all participants enrolled in the rest/stress group will come to the CCIR facility for <24-hours for screening, pre and post rest/stress [⁶⁸Ga]Galmydar PET MPI safety assessments.

On Imaging Day-2, all participants will report directly to the CCIR facility for the rest/stress ¹³N-Ammonia PET MPI. [⁶⁸Ga]Galmydar and ¹³N-ammonia imaging visits will be separated by a minimum of 3-days and not before the follow-up phone call is complete for capturing participant adverse events following the administration of ⁶⁸Ga-Galmydar.

In some instances, participants may be split the Day-1 imaging into two visits and complete a Day-3 study. Therefore, on imaging Day-1, participants enrolled in the rest/stress group will come to the CCIR for screening, pre [⁶⁸Ga]Galmydar PET MPI safety assessments and the rest imaging. On Day-2 participants will return to the CCIR for their stress imaging and post [⁶⁸Ga]Galmydar PET MPI safety assessments. On Imaging Day-3, participants will report to the CCIR facility for the rest/stress ¹³N-Ammonia PET MPI.

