6.4.2.1 Rest ¹³N-Ammonia PET

- Review of concomitant medications and any changes in health between the rest/stress PET MPI imaging day-1, ⁶⁸Ga-Galmydar, and imaging day-2, ¹³N-ammonia;
- Confirm a negative urine pregnancy test for women of childbearing potential;
- Obtain baseline vital signs (BP and HR) pre and post ¹³N-ammonia injection as described above. Continue to monitor ECG-rhythm and HR until imaging is completed;
- Administer an intravenous bolus injection of 10 mCi \pm 20% (8–12 mCi) of ¹³N-ammonia followed by a 10 mL normal saline flush.
- Begin a 10-min list-mode data acquisition (if the anterior-posterior diameter of the chest is >50 cm increase to 15-min) for a single bed position at the level of the heart immediately post-injection;
- Obtain vital signs (BP and HR) and 12-lead ECG as required per clinical protocol;
- Remove patient from scanner for a break. The interval between the rest and stress ¹³N-ammonia acquisitions should be per the clinical protocol (*no less than 1-hour*).

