7.4.2 Rest/Stress group

Rest/stress participants will receive a phone call within 2-3 days post [⁶⁸Ga]Galmydar injection. The follow-up phone call to collect safety data must be complete before scheduling a participant for the rest/stress ¹³N-ammonia PET imaging visit.

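### Galmydar always comes before ammonia, and no period or hemodynamic adjustment is planned, so a systematic visit difference would be read as a tracer difference in rest MBF and MFR

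*Combined protocol and SAP*

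**What the plan says.** Section 6.4 gives one sequence for the whole rest/stress group. Galmydar comes first: "On Imaging Day-1, all participants enrolled in the rest/stress group will come to the CCIR facility" for screening and the Galmydar rest and stress studies. Ammonia comes second: "On Imaging Day-2, all participants will report directly to the CCIR facility for the rest/stress" ammonia study. If the Galmydar study is split over two visits, ammonia is still last: "On Imaging Day-3, participants will report to the CCIR facility for the rest/stress" ammonia study.

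Section 7.4.2 builds the order into scheduling: "The follow-up phone call to collect safety data must be complete before scheduling a participant for the rest/stress" ammonia visit. Sections 6.4 and 6.4.2 and the notes to Table 3 add a gap of at least 3 days, with no maximum.

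Blood pressure and heart rate are taken around both rest scans. For Galmydar, Section 6.2.1 has "Pre-injection: BP, HR, and RR within 15-min", and Section 6.4.1.1 repeats a reading in that window. For ammonia, Section 6.4.2.1 has "Obtain baseline vital signs (BP and HR) pre and post" injection.

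The primary objective (Section 2.1) includes quantitative MBF by Galmydar against ammonia. Section 8.1.4 derives MFR and fits the Galmydar extraction parameters by relating its K1 to microsphere and ammonia MBF. Section 9 mentions no period effect, no hemodynamic correction and no named analysis of MBF agreement.

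**The concern.** This is a paired comparison with a single sequence, so tracer and visit change together in every participant. The visits are not alike by design. The Galmydar visit normally carries screening and the first regadenoson stress of the study, while at the ammonia visit participants report directly for imaging. If resting flow follows cardiac work, a systematically higher heart rate or pressure at the first visit would raise rest MBF and lower MFR for Galmydar alone. A difference in the other direction would do the reverse, and either could mask a real tracer difference.

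The same offset could pass into the K1 calibration. The protocol describes no microsphere procedure in humans, so ammonia is the only in-human reference for that fit.

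Missing data also fall unevenly. Losses after a first-visit event fall mainly on the ammonia visit, which takes paired stress MBF and MFR values out of the comparison.

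**Working it through.** **The plan's own figure.** Section 9.1 gives a 95% interval for kappa of 0.669 to 0.931 (width 0.26) from n = 20, kappa 0.8 and SD 0.3. The check is 0.8 ± 1.96 x 0.3/√20 = 0.8 ± 0.1315, or 0.6685 to 0.9315, width 0.263. It reproduces. It does not involve visit order and says nothing about MBF precision.

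**Identifiability.** Let τ be the tracer effect and δ the systematic first-minus-second-visit effect. The expected Galmydar-minus-ammonia difference is τ + δ for a participant who has Galmydar first and τ − δ for one who has ammonia first.
- As planned, all 30 are Galmydar-first. The design has rank 1 for two parameters, and the mean difference estimates τ + δ.
- With 15 in each order, the rank is 2. Both effects can be estimated, and the variance factor for τ stays at 1/30.

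**Illustration for MFR.** Assumption: rest MBF is proportional to heart rate x systolic pressure, and stress MBF is unaffected. MFR = stress MBF / rest MBF, so a product higher by a fraction x multiplies MFR by 1/(1 + x).

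| Product at first visit | Rest MBF | MFR factor | MFR reads low by |
|---|---|---|---|
| +5% | x 1.05 | 1/1.05 = 0.952 | 4.8% |
| +10% | x 1.10 | 1/1.10 = 0.909 | 9.1% |
| +15% | x 1.15 | 1/1.15 = 0.870 | 13.0% |

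Under the same assumption, dividing rest MBF by the rate-pressure product of its own scan removes the offset (for example, 1.10/1.10 = 1).

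**Systematic versus random.** Paired tests were simulated at n = 30 (40,000 trials per setting, two-sided 5%, no true tracer difference). The within-subject CV of MBF and the visit effects are assumptions. The SD of the paired difference is √2 x CV.

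| Assumed CV | No visit effect, fixed order | 5% effect, fixed order | 10% effect, fixed order | Any of these, 15/15 order |
|---|---|---|---|---|
| 10% | 5% | 46% | 96% | about 5% |
| 15% | 5% | 24% | 71% | about 5% |
| 20% | 5% | 16% | 47% | about 5% |
| 25% | 5% | 12% | 32% | about 5% |

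Entries are the chance of declaring a tracer difference. Without a systematic effect the fixed order has no bias. Random variation only widens agreement, with limits of about ±28% (CV 10%) to ±69% (CV 25%) of mean MBF in either order.

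**Which data can be lost.**
- Section 4.5: after a regadenoson event at stress, if the investigator judges the participant ineligible for ammonia stress, "The participant will only undergo the rest portion of the" ammonia study. Only ammonia stress is lost.
- Section 6.4.2: a clinical change between visits may lead to rest-only ammonia or to rescheduling.
- Section 7.3: second- or third-degree AV block or QTc ≥ 500 after injection ends further procedures. After the Galmydar rest injection, this removes Galmydar stress and both ammonia scans. After the Galmydar stress injection, it removes both ammonia scans.
- Section 4.6: participants with incomplete procedures are replaced. It is not stated whether a participant with rest-only ammonia counts as incomplete. If so, replacement favors people who tolerated the first stress test.

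**The case against.** The strongest reply is that visits are partly standardized and nothing shows a visit effect exists. Section 6.2.1 requires fasting, a hold on vasoactive drugs and a quiet period before the scout image. Section 6.4.2 checks symptomatic patients for clinical change before ammonia. Screening may fall on a separate day, Table 3 marks IV placement on both imaging days, and the split option moves Galmydar stress off the first visit. The study is phase 0/1, MBF is one component of the primary objective, and Section 9 names kappa on diagnostic classification rather than a test of mean MBF. All of this stands. It limits the likely size and the stakes, but it does not make a visit effect estimable.

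A reader might infer four stronger points that the documents do not support:
- That only ammonia stress data can be lost. Section 7.3 can also remove Galmydar stress and ammonia rest, and the Section 4.5 rule depends on the investigator's judgment.
- That all day-to-day hemodynamic variation is confounded with tracer. Only its systematic part is.
- That Galmydar MFR will be 5% to 15% off. Size, direction and exact proportionality are assumptions, and the K1 calibration to ammonia flow could absorb part of any offset.
- That tracer order could be randomized with the safety call left as written. Section 7.4.2 requires the call before the ammonia visit is scheduled, which nobody imaged first with ammonia could satisfy.

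**Conclusion.** The point holds in a limited form. The order is the same for everyone, and neither design nor analysis separates a systematic visit effect from tracer in the rest MBF and MFR comparison. The effect could also enter the K1-to-ammonia fit. Its size and direction cannot be found from the documents. The 4.8% to 13% range for MFR rests on an assumed 5% to 15% difference in rate-pressure product and on proportionality of rest flow to that product. The false-difference rates also rest on assumed CVs and on a paired mean test that Section 9 does not name. The sample-size calculation is unaffected. Losses after a first-visit event fall mainly, not exclusively, on ammonia.

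The readings needed to reduce one identifiable source of visit bias are already collected, so leaving them out of the analysis is avoidable.

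**What to change.** In Sections 8.1.4 and 9, before analysis:

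1. Pre-specify that the Galmydar-versus-ammonia comparison of rest MBF and MFR is reported twice: uncorrected, and with rest MBF normalized to the heart rate x systolic pressure recorded at that rest scan. Fix one reference constant for all scans and name the reading used, because Section 6.4.2.1 gives the ammonia reading no explicit time window.
2. Tabulate rest heart rate and blood pressure by visit.
3. State that the fixed order leaves any remaining visit effect inseparable from tracer. The normalization addresses only the part at rest that acts through heart rate and pressure.

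The cost is a few lines of text and one table, with no new procedure, visit or participant.

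Randomizing tracer order is an option for the sponsor to consider, not a required change. It would make the two effects separable, but Sections 4.5, 6.4, 6.4.2 and 7.4.2 and the Table 3 notes are all written for Galmydar first and would have to be reconciled through an amendment. Ammonia would also have to be available for first visits.
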